3.1 Sample Size

Approximately 95 subjects are expected to be enrolled into the 2-week, single-blind (subject blind) Screening Placebo Run-In Period. It is expected that 20% of subjects will not qualify for randomization after Screening Placebo Run-In.

The study is expected to randomize approximately 78 subjects into the double-blind treatment where subjects will be allocated to litoxetine (dose titration over 10 mg, 20 mg, 30mg) or matched placebo BID in a 2:1 ratio. A post randomisation dropout rate of 30% has been estimated, resulting in 60 evaluable subjects.

A sample size of 60 subjects is expected to provide a 95% confidence interval for a rate of safety events of 50% with a width +/- 14%. The sample size calculation is based on the precision of the estimate of the primary outcome, safety events, using a rate of 50% which would provide the most conservative sample size.

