6.2 Covariate and Subgroups

Safety

Age (under 65, over 65) is used as subgroup for the analysis of treatment emergent adverse event.

Efficacy

The methodology described in the protocol for the efficacy analyses is a mixed model with repeated measures (MMRM). In light of the fact that the efficacy measurements were recorded at visit 2 and visit 6 only, there are no repeated measures. Therefore, the MMRM model described in the protocol cannot be applied to these analyses. The efficacy analyses will be conducted as an analysis of covariance (ANCOVA).

The model will include Baseline values as a covariate and dose and site as factor variables.

Baseline is defined as end of Screening Placebo Run-in for all efficacy analyses (Visit 2).

Exploratory efficacy analysis will be performed based on the baseline severity of incontinence episodes, as defined in section 5.4.2. Patients will be divided in 2 groups according to the median number of incontinence episodes.

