Categorical variables will be summarised by using frequency distributions and percentages.

For all analyses, hypothesis testing will be carried out at the alpha = 0.05 level (two-sided) when comparing treatments. P-values will be rounded to three decimal places. Statistical significance will be declared if the rounded p-value will be less than or equal to 0.05.

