6.9 Efficacy Analyses

Efficacy will be assessed by the number of urinary incontinence episodes. There is only one hypothesis so there will be no adjustment for multiplicity.

The efficacy analysis will be performed on the ITT and PP populations.

There will not be an adjustment for multiple comparisons for these efficacy analyses.

Baseline for all efficacy endpoints will be defined as the last week of the Screening Placebo Run-In Period (Visit 2). The final measurement (endpoint) will be defined as Week 8 (Visit 6).

1. Percentage change from end of the Screening Placebo Run-In Period to Week 8 in the number of incontinence episodes in a week

The efficacy analysis planned is an analysis of covariance model (ANCOVA). Percentage change in the number incontinence episodes/week is the response variable. The factor variables will be dose and centre. If the center effect is significant, summary statistics will be presented to describe the effect. The covariate will be end of the Screening Placebo Run-In Period episodes of incontinence.

The percentage change, $\%UIE_i$, for subjects in each arm, is expressed as the ratio of the total number of urinary incontinence episodes in a week between final measurement ($UIE_{i,end}$) and baseline ($UIE_{i,base}$)

$$\%UIE_i = \frac{UIE_{i,end}}{UIE_{i,base}}$$

Since percentage change from baseline does not have the properties of additivity and symmetry, it will be log-transformed, and the response variable will be the natural logarithm of the ratio of Week 8 (Visit 6) to Baseline, as shown below:

$$\log(\%UIE_i) = \log\left(\frac{UIE_{i,end}}{UIE_{i,base}}\right)$$

The hypothesis test being conducted is as follows:

$$\begin{aligned} H_0: \log(\%UIE_{\text{Litoxetine}}) - \log(\%UIE_{\text{Placebo}}) &= 0 \\ H_1: \log(\%UIE_{\text{Litoxetine}}) - \log(\%UIE_{\text{Placebo}}) &\neq 0, \end{aligned}$$

This is equivalent to testing the hypothesis:

$$H_0: \log\left(\frac{\%UIE_{Litoxetine}}{\%UIE_{Placebo}}\right) = 0$$

The result of the ANCOVA model will be expressed as log % and then back transformed to percentage change. Therefore, H_0 can be interpreted as:

$$H_0: \frac{\%UIE_{Litoxetine}}{\%UIE_{Placebo}} = 1$$

This makes the actual statistics:

$$\delta = \log(\%UIE_{Litoxetine}) - \log(\%UIE_{Placebo}) = \log\left(\frac{\%UIE_{Litoxetine}}{\%UIE_{Placebo}}\right)$$

When back-transformed, this is expressed as follows:

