6.9.2 Exploratory Efficacy Analyses

The severity of incontinence episodes will be explored dividing the population in subjects with less/more severe UI. Less severe is defined as the population who has incontinence episode frequency below the study median at baseline, while more severe is defined as the population who has incontinence episode frequency above the study median at baseline.

Based on the assessment of the variability of the data and the size of each subgroup, the efficacy analysis will be performed on the subgroups.

Baseline severity threshold is defined as the median value of incontinence episodes at baseline.

These analyses will be performed on the PP population only.

1. Percentage change from end of the Screening Placebo Run-In Period to Week 8 (Visit 6) in the number of incontinence episodes in a week as a function of degree of incontinence

The percentage change in the total number of incontinence episodes in a week will be analysed with an ANCOVA model. It will follow the efficacy analysis described in section 6.9 point 1. Patients will be divided in two groups depending on the baseline severity of incontinence episodes.

The median number of incontinence episodes at baseline will be computed on the randomised population. Two analyses will be performed, one on subjects whose baseline number of incontinence episodes is less than the median, and the other on subjects whose baseline number of incontinence episodes is greater than or equal to the median.

2. Change from end of the Screening Placebo Run-In Period to Week 8 (Visit 6) in the number of incontinence episodes/24 hours (daily average) as a function of degree of incontinence.

The change in the number of incontinence episodes/24 hours (daily average) will be analysed with an ANCOVA model. It will follow the efficacy analysis described in section 6.9 point 2. Patients will be divided in two groups depending on the baseline severity of incontinence episodes.

The median number of incontinence episodes at baseline will be computed on the randomised population. Two analyses will be performed, one on subjects whose baseline number of incontinence episodes is less than the median, and the other on subjects whose baseline number of incontinence episodes is greater than or equal to the median.

7. General Considerations

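### The severity analysis in SAP 6.9.2 runs two separate subgroup tests with no treatment-by-severity interaction, so it cannot show whether the effect depends on severity

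*SAP*

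**What the plan says.** SAP 6.9.2 divides subjects into less and more severe incontinence at the median baseline episode count, taken from the randomised population. For each of two endpoints (percentage change in weekly episodes, absolute change in episodes per 24 hours) it plans separate models: "Two analyses will be performed, one on subjects whose baseline number of incontinence episodes is less than the median", the other on those at or above it. Of the first endpoint it says "It will follow the efficacy analysis described in section 6.9 point 1"; the second follows point 2 of the same section. Both models contain treatment and centre as factors ("The factor variables will be dose and centre") with baseline episodes as covariate. On the analysis set: "These analyses will be performed on the PP population only".

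The inferential rule is general. SAP 6.3 states: "For all analyses, hypothesis testing will be carried out at the alpha = 0.05 level (two-sided) when comparing treatments". SAP 6.9 adds: "There will not be an adjustment for multiple comparisons for these efficacy analyses".

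SAP 5.4.2 labels the analysis exploratory and says that earlier litoxetine results prompted it. SAP 6.9.2 makes it depend on a look at data variability and subgroup size, with no threshold. Neither document specifies a treatment-by-severity term, a contrast between the two subgroup effects, or a rule for reading them together.

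**The concern.** Whether benefit changes with severity is a question about the difference between two treatment effects. Two within-subgroup tests ask something else: whether each effect differs from zero. In small halves, one can cross 0.05 and the other miss it by chance when the underlying effect is the same in both.

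Within this analysis, the subgroup estimates and their p-values are the only output that bears on severity. Because the question comes from an earlier signal, a chance split in significance could pass for confirmation of it. What is at stake is the interpretation of an exploratory efficacy analysis, and any later choice of population that leans on it. The primary safety conclusions are not touched.

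**Working it through.** **Plan's own figures.** The documents give no power, effect size or error rate for this analysis. The nearest stated figure is the evaluable number. SAP 3.1 says "The study is expected to randomize approximately 78 subjects into the double-blind treatment" and expects 60 evaluable after 30% dropout. But 78 × 0.7 = 54.6, so 60 is not reproduced (78 / 1.3 = 60). That is a separate matter; here both 54 and 60 are carried as the per-protocol size.

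**Inputs.**
- Allocation 2:1 (SAP 3.2).
- Two-sided alpha 0.05 (SAP 6.3).
- Equal halves: 27 subjects (18 vs 9) or 30 subjects (20 vs 10).
- Standardised effect d, the same in both halves: assumed, 0 to 1.0 SD.

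**Step 1: power in one half, without site terms.** The model has intercept, treatment and baseline, so df = 27 − 3 = 24 or 30 − 3 = 27. The noncentrality is d / √(1/n₁ + 1/n₂). For 18 vs 9 at d = 0.8 it is 0.8 / 0.408 = 1.96, and the noncentral t gives power s = 0.47.

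**Step 2: exactly one of two independent halves significant** = 2s(1 − s).

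| Uniform effect (SD) | Power per half, N = 54 / 60 | Exactly one significant, N = 54 / 60 |
|---|---|---|
| 0 | 5% / 5% | 9.5% / 9.5% |
| 0.2 | 7.6% / 7.9% | 14.0% / 14.5% |
| 0.5 | 22% / 24% | 34% / 36% |
| 0.8 | 47% / 51% | 50% / 50% |
| 1.0 | 65% / 70% | 45% / 42% |

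The expression 2s(1 − s) cannot exceed 50%, which it reaches at s = 0.5. An effect of 0.8 SD therefore sits on the peak.

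**Step 3: comparison with an interaction test.** A simulation (2,000 runs per setting, N = 54 or 60, median split, common effect in both halves) fitted one model with a treatment-by-severity interaction. It rejected in 4.1% to 5.5% of runs in every setting, that is, at the nominal 5%.

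**Step 4: the SAP model with site terms.** The protocol synopsis allows up to 15 sites. The simulation used 10 or 15, with subjects spread at random over sites and randomisation not stratified by site. Exactly one half was significant in about 9% of runs at d = 0, 24-30% at 0.5, 39-45% at 0.8 and 45-51% at 1.0. At 0.5 and 0.8 these are lower than the simulated rates without site terms (32-37% and 50%), because site terms cost power in each half.

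**Step 5: what an interaction test can detect.** For a median-split interaction at N = 54, the standard error of the difference between the two effects is √[2 × (1/18 + 1/9)] = 0.577 SD. With 54 − 5 = 49 df the 95% CI half-width is 2.01 × 0.577 = 1.16 SD. Power is about 14% for a 0.5 SD difference between halves and 27% for 0.8 SD.

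**The case against.** The strongest reply is that this is an exploratory look within a secondary objective, in a trial whose primary purpose is safety. The SAP speaks of exploring severity, makes the analysis depend on subgroup size and variability, and contains no rule that declares a severity effect when only one half is significant. All of that is correct. It limits the weight of the point but does not supply a valid way to answer the question.

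A reader might infer that a spurious severity difference is likely. The documents do not support that. With no effect the rate is about 10%. The 50% figure is the mathematical ceiling, reached at an effect size that appears nowhere in the documents. It also requires someone to compare the two p-values, which the SAP does not say will happen.

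A reader might also blame the centre terms ("The model will include Baseline values as a covariate and dose and site as factor variables") for the discordance. They do not cause it: at 0.5 and 0.8 SD they lower it, and with no effect they leave it at about 9%. Their cost is precision. In the simulation, error df per half fell from 24-27 to about 12-18, and 28-46% of subjects were in sites with only one arm in that half. Those figures rest on assumed site numbers and unstratified randomisation; the assignment details are in a separate document. Whether to keep, pool or drop site is a question for the main ANCOVA.

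Finally, an interaction test here has little power. That is true, and is why the recommendation rests on the estimate and its interval.

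**Conclusion.** The point holds in a limited form. As written, SAP 6.9.2 cannot show whether the effect depends on severity, because it never estimates or tests the difference between the two subgroup effects. This follows from the text and needs no assumption.

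The size of the risk is conditional. If the two p-values are compared, the chance that exactly one half is significant under a uniform effect runs from about 10% (no effect) to about 50%, against about 5% for an interaction test. This assumes equal halves of a per-protocol set of 54 to 60, 2:1 allocation within each half, no site terms, and effects of 0 to 1.0 SD. The per-protocol set may be smaller. The halves may also be unequal, since the median comes from the randomised population. The change is worth making because it is nearly free.

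**What to change.** For each of the two endpoints in SAP 6.9.2:
- Fit one ANCOVA as specified in section 6.9, adding a treatment-by-baseline-severity interaction with baseline episodes kept continuous.
- Report the interaction estimate with its 95% CI.
- Keep the median-split results as a descriptive display (estimates with CIs), and state that they are not to be compared by p-value.
- Repeat in the ITT population as a supportive display.
- State in advance that a non-significant interaction will not be read as evidence of a uniform effect.

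The cost is SAP wording and one extra model per endpoint, plus its ITT repeat. No new data are needed. The limitation is the low power and wide interval shown in the working. Site terms should follow whatever is settled for the main ANCOVA; no change to them is proposed here.

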7.1 Software to be used

All statistical analyses and data processing will be performed using SAS version 9.4 or higher.

